7.1.2 Derived Datasets and Variables

Derived datasets will be generated according to GDDB Implementation Guide (G-SPEC-RD-004), version 01 (30 April 2011). Following are definitions of derived variables:

- Body mass index (BMI) will be calculated as weight (kg)/(height (m))² and will be presented to 1 decimal place. BMI will be calculated for Screening.

7.1.3 Definition of Study Days and Baseline

Study Day 1 is defined as the date on which a subject is administered their first dose of the medication. Other study days are defined relative to the Study Day 1 with Day 1 being Study Day 1 and Day -1 being the day prior to Study Day 1.

- If the date of the event is on or after the date of first dose:
Study Day = date of event – date of first dose +1.
- If the date of the event is prior to the date of first dose:
Study Day = date of event – date of first dose.

Baseline values are defined as the last observed value before the first dose of study medication (including a screening value and unscheduled assessments if necessary). In the case where the last observed value and the first dose coincide, that value will be considered as baseline value, unless actual time (hour: minute) indicate otherwise. Unless otherwise specified, AEs and medications commencing on the first dose date (i.e. Study Day 1) will be considered as post baseline events, unless actual time (hour : minute) indicate otherwise.

7.1.4 Statistical Software

All statistical analyses will be conducted using SAS® Version 9.2, or higher.

7.2 Analysis Sets

Randomized Set: The randomized set will include all subjects who are randomized.

Safety Set: The safety set will include all randomized subjects who received at least 1 dose of study drug, including subjects who do not complete the study.

Pharmacokinetic Set: The pharmacokinetic set will consist of all subjects who received study drug and have at least 1 measurable plasma concentration for TAK-536. If any subjects are found to have incomplete data, a decision will be made on a case-by-case basis as to their inclusion in the analysis, but will be presented in the subject listings.

7.3 Disposition of Subjects

Study Information, including date first subject signed ICF, date of first and last open-label dose, date of first and last double-blind dose, date of last subjects' last visit/contact for open-label part and double-blind part, Medical Dictionary for Regulatory Activities (MedDRA) Version, World Health Organization (WHO) Drug Dictionary Version, and SAS Version will be presented.

All screened subjects will be presented, number of subjects who signed informed consent, number of subjects who were or not randomized and primary reason for screen failure (pretreatment event/adverse event, significant protocol deviation, lost to follow-up, voluntary withdrawal, study termination, did not meet entrance criteria or other) will be summarized as recorded on the eCRF.

Disposition of all randomized subjects will be tabulated by randomized regimen and study part.

Subjects with significant protocol deviations will be summarized, and categories will be tabulated as entered on the eCRF. Number of subjects within each analysis set will be tabulated.

7.4 Demographic and Other Baseline Characteristics

Demographic and baseline characteristics will be summarized and listed by regimen for each part and overall using the Randomized Set. Demographic and baseline characteristics will include age (years) at date of informed consent, gender, race, height (cm), baseline weight (kg), baseline body mass index (BMI) (kg/m²), smoking classification, and female reproductive status.

Summary statistics (N, mean, SD, median, minimum, and maximum) will be generated for continuous variables (eg, age, height, weight and BMI), and the number and percentage of subjects within each category will be presented for categorical variables (eg, gender, race, ethnicity, smoking classification and female reproductive status). Individual demographic and baseline characteristics will be listed by study part and regimen.

Demographic variables of screen failure subjects and reasons for screen failures will be summarized for all subjects who are screened but not enrolled in the study. Individual demographic characteristics, date of informed consent, any available safety data and reason for screen failure will also be presented in the data listing.

7.5 Medical History and Concurrent Medical Conditions

Medical history (significant conditions or diseases that stopped at or prior to the time of informed consent) and concurrent medical conditions will be listed. Medical history and concurrent medical conditions will be coded as system organ class (SOC) and preferred term (PT) using the MedDRA, Version 19.0, or higher coding system.

All medical history and concurrent medical condition data will be listed by study part, regimen, site number and subject number.

7.6 Medication History and Concomitant Medications

Medication history and concomitant medications will be listed

Medication history information to be obtained includes any medication relevant to eligibility criteria stopped at or within 28 days prior to signing of informed consent.

Concomitant medications are recorded on the eCRF and include any medication other than study drug taken at any time between time of informed consent through the end of the study (including the follow-up visit).

Medication history and concomitant medications will be coded using the World Health Organization (WHO) Drug Dictionary (Version 01March2014, Enhanced, or higher) coding system.

Separate listings for medication history and concomitant medications will be produced by study part, regimen and site number and subject number.

7.7 Study Drug Exposure and Compliance

The date and time of each dose for each subject will be reported in the data listing for all subjects. Summaries of PK data will be provided by regimen. No other summary statistics for the extent of exposure to study drug or compliance calculations will be performed for this study.

7.8 Efficacy Analysis

Not applicable.

7.8.1 Primary Efficacy Endpoint(s)

Not applicable.

7.8.2 Secondary Efficacy Endpoint(s)

Not applicable.

7.8.3 Additional Efficacy Endpoint(s)

Not applicable.

7.9 Pharmacokinetic/Pharmacodynamic Analysis

7.9.1 Pharmacokinetic Concentrations

Serial blood samples for determination of TAK-536 will be collected according to [Table 7.a](#).

Table 7.a Collection of Blood Samples for TAK-536 Pharmacokinetic Analysis

Matrix	Dosing Day(s)	Scheduled Time
Plasma	1	Predose (up to 15 minutes prior to dose [0 hour]) and at 0.5, 1, 2, 3, 4, 6, 8, 12, 16, 24, 36, 48, and 72 hours postdose
Plasma	7, 8, 9	Predose (up to 15 minutes prior to dose [0 hour])
Plasma	10	Predose (up to 15 minutes prior to dose [0 hour]) and at 0.5, 1, 2, 3, 4, 6, 8, 12, 16, and 24 hours postdose

Serial urine samples for determination of TAK-536 will be collected according to [Table 7.b](#).

Table 7.b Collection of Urine Samples for TAK-536 Pharmacokinetic Analysis

Matrix	Dosing Day	Scheduled Time
Urine	1	Predose (-12 to 0 hour) and at 0 to 2, 2 to 4, 4 to 8, 8 to 12, 12 to 24, 24 to 48, and 48 to 72 hours postdose
Urine	10	0 to 2, 2 to 4, 4 to 8, 8 to 12, and 12 to 24 hours postdose

All pharmacokinetic analyses will be based on Pharmacokinetic Set.

Concentrations of TAK-536 in plasma and the amount of TAK-536 excreted in urine will be summarized by regimen over each scheduled sampling time using descriptive statistics (N, mean, SD, SE, median, minimum and maximum) for the open-label and double-blind parts separately. Individual plasma and urine concentrations data will be listed.

7.9.2 Pharmacokinetic Parameters

Plasma and urine PK parameters of TAK-536 are listed in [Table 7.c](#).

Table 7.c Pharmacokinetic Parameters

Symbol/Term	Definition
Plasma	
AUC ₂₄ (h* ng /mL)	Area under the concentration-time curve from time 0 to 24 hours (multiple dose only).
AUC _{last} (h*ng/mL)	Area under the concentration-time curve from time 0 to time of the last quantifiable concentration (single dose only).
AUC _∞ (h*ng/mL)	Area under the concentration-time curve from time 0 to infinity (single dose only), calculated using the observed value of the last quantifiable concentration.
C _{av,ss} (ng/mL)	Average concentration during a dosing interval at steady state (multiple dose only).
C _{max} (ng/mL)	Maximum observed concentration.
C _{min} (ng/mL)	Minimum observed concentration during a dosing interval (multiple dose only).
C _{trough} (ng/mL)	Observed concentration at the end of a dosing interval (multiple dose only).
λ _z (1/h)	Terminal disposition phase rate constant (single dose only).
t _{1/2z} (h)	Terminal disposition phase half-life (single dose only).
t _{max} (h)	Time of first occurrence of C _{max} .
Urine	
Ae _{t₁-t₂} (mg)	Amount of drug excreted in urine from time 1 to time 2.
Ae _t (mg)	Amount of drug excreted in urine from time 0 to time t.
f _{et} (%)	Fraction of administered dose of drug excreted in urine from time 0 to time t.
CL _R (L/h)	Molecular weight adjustment needed for metabolites Renal clearance.

Plasma and urine PK parameters of TAK-536 will be summarized by regimen using descriptive statistics (N, mean, SD, SE, %CV, median, minimum and maximum) for each part separately. Geometric means (GM) and %GM CV will also be computed for AUCs, C_{max} and C_{min}. All individual PK parameters data will be listed.

Additional plasma PK parameters and/or analyses may be added in the presentation as considered appropriate.

7.9.3 Pharmacodynamic Analysis

Not applicable.

7.10 Other Outcomes

Not applicable.

7.11 Safety Analysis

Safety summaries will be based on the Safety Set. All safety assessments, including AEs, clinical laboratory evaluations, 12-lead ECG results, physical examination, and vital signs will be summarized with descriptive statistics by regimen for each part separately and overall, where appropriate, and presented in the data listings.

7.11.1 Adverse Events

Pretreatment events (PTEs) and AEs will be coded using MedDRA Version 19.0 or higher.

A PTE is defined as any untoward medical occurrence in a clinical investigation subject who has signed informed consent to participate in a study, but prior to administration of any study medication; it does not necessarily have to have a causal relationship with study participation.

An AE is defined as any untoward medical occurrence in a clinical investigation subject administered a pharmaceutical product, including placebo; it does not necessarily have to have a causal relationship with this regimen.

Treatment-emergent adverse events (TEAE) are defined as any AEs, regardless of relationship to study drug, which occurred or worsened in severity on or after the first dose of study medication and until 30 days after the last dose of study medication is received.

When calculating the frequency and percentage of subjects who reported TEAEs, a subject will be counted only once for each SOC or PT when multiple TEAEs are coded to the same SOC or PT. Thus, if a subject has two distinct AEs, each of which corresponds to a distinct PT but both of which correspond to the same SOC, then that subject will be counted once at that SOC subject-count summary level and once at each of the two PTs subject-count summary levels. For the intensity summaries, if a subject reports multiple TEAE coded to the same SOC or PT, the TEAE with maximum intensity will be included in the summary. For the relationship summaries, if a subject reports multiple TEAEs coded to the same SOC or PT, the TEAE most related to study drug will be included in the summary.

Adverse events will be summarized by study part, regimen and TAK-491 overall for double blind part, which will include the number and percentage of subjects as follows:

- Overview of Treatment-Emergent Adverse Events
- Treatment-Emergent Adverse Events by System Organ Class and Preferred Term
- Subject Mappings for Treatment-Emergent Adverse Events
- Treatment-Emergent Adverse Events by Preferred Term
- Non-Serious Treatment-Emergent Adverse Events by and Preferred Term
- Relationship of Treatment-Emergent Adverse Events by System Organ Class and Preferred Term
- Drug-Related Treatment-Emergent Adverse Events by System Organ Class and Preferred Term

- Intensity of Treatment-Emergent Adverse Events by System Organ Class and Preferred Term
- Intensity of Drug-Related Treatment-Emergent Adverse Events by System Organ Class and Preferred Term
- Pretreatment Adverse Events (PTE) by System Organ Class and Preferred Term
- Pretreatment Serious Events by System Organ Class and Preferred Term

7.11.2 Clinical Laboratory Evaluations

Clinical laboratory tests will be evaluated by central laboratory and presented using the International System of Units (SI) units unless otherwise stated. [Table 4.c](#) shows the scheduled measurements for clinical laboratory tests and [Table 7.d](#) shows a list of all clinical laboratory tests.

Table 7.d Clinical Laboratory Tests

Hematology	Serum Chemistry	Urinalysis
Red blood cells	Alanine aminotransferase	pH
White blood cells with differential (neutrophils, eosinophils, basophils, lymphocytes, monocytes)	Albumin	Specific gravity
Hemoglobin	Alkaline phosphatase	Protein
Hematocrit	Aspartate aminotransferase	Glucose
Platelets	Total bilirubin	Blood
	Total protein	Ketones
	Creatinine	Microscopic Analysis (a):
	Blood urea nitrogen	RBC/high power field
	Creatine kinase	WBC/high power field
	γ -Glutamyl transferase	Epithelial cells, casts etc.
	Potassium	
	Sodium	
	Glucose	
	Chloride	
	Triglycerides	
	HDL-C	
	LDL-C	
	Total cholesterol	
Diagnostic Screening:		
Serum	Urine	Breath
HBsAg, anti-HCV, anti-HIV (b) Additional Virology Tests: Anti-HBsAb, HBeAg, anti-HBeAb, anti-HBcAb, EBV VCA IgG, EBV VCA IgM, Anti-CMV IgG, and Anti-CMV IgM (c)	Drug screen, including amphetamines, barbiturates, benzodiazepines, cannabinoids, cocaine, opiates, and cotinine	Breath alcohol test
Female Subjects only:		
Serum hCG at Screening, Check-in, and Study Exit or Early Termination		

EBV= Epstein-Barr virus viral capsid antigen, hCG=human chorionic gonadotropin, RBC=red blood cell, WBC=white blood cell.

(a) Microscopic analysis should be performed only if urine evaluations are abnormal.

(b) HBsAg, anti-HCV, and anti-HIV test results will be collected for all subjects.

(c) The results for the additional virology tests performed at Screening will be recorded in the (e)CRF for randomized subjects only.

The following summaries will be provided for laboratory data by part and regimen:

- Baseline, postdose, and, change from baseline to postdose values for quantitative measurements.
- Number and percent of urine parameters results for categorical measurements.
- Number and percent of subjects with markedly abnormal value (MAV) which identified by the criteria in [Appendix A](#).
- Shift from baseline of high/low/normal values according to normal range criteria (baseline versus each post-baseline visit).

If a subject has multiple values within a particular visit window, the most abnormal result will be used for summary.

All clinical laboratory results data will be presented by subject in listing.

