6.2 Justification for Study Design, Dose, and Endpoints

This randomized, open-label and double-blind, placebo-controlled, single- and multiple-dose, phase 1 study was designed with the following justification. The parameters listed as primary endpoints are considered appropriate for evaluation of pharmacokinetic profiles associated after single- and multiple-doses, and the additional safety endpoints comprise established safety assessments recognized as reliable, accurate, and relevant.

The pharmacokinetics of TAK-536 after administration of TAK-491 has been thoroughly characterized from data collected during the phase 1 clinical pharmacology program conducted in the United States and Europe. The $t_{1/2z}$ for TAK-536 following TAK-491 administration is approximately 11 hours; the planned sampling scheme after the single dose is approximately 6 half-lives and appropriate. Steady state of TAK-536 is achieved within 5 days of dosing of TAK-491; the multiple-dose duration is appropriate. A total of 64 healthy subjects will be enrolled into the study. An open-label design was used during the dosing of the first 16 subjects (in 2 consecutive cohorts) because the primary outcomes are based on objective measurements, that is, plasma concentrations of TAK-536. Fifteen of these first 16 subjects had a higher ALT and/or AST level on Day 11 than on Day -1. While none of these subjects had Day 11 ALT and/or AST values that exceeded 3×ULN of protocol mandated monitoring criteria (see [Section 7.5](#) [No.1] and [Section 10.2.3](#)), 7 of these exceeded the ULN. None of these ALT/AST elevations were accompanied by symptoms or signs of liver injury or by bilirubin elevation, and resolved without intervention. High frequency of subjects with elevations in ALT and/or AST levels were unexpected and unprecedented, as no similar findings were observed in previous TAK-491 phase 1 through 3 studies with the enrollment of subjects from different races and ethnicities (ie, Caucasians, African Americans, Mexican Americans, Native Americans, Asians, and other ethnicities). While other procedure-related factors, such as high-carbohydrate diet and minimal physical activity during the confinement period in the phase 1 unit, as described in the medical literature [\[10-12\]](#), might have been accountable for these asymptomatic ALT/AST elevations in the present study, a potential drug-related phenomenon has to be definitively ruled out. Hence, a

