Appendix F Detailed Description of Amendments to Text

Rationale for Amendment

Protocol Amendment 3, dated 18 March 2016 was submitted to the EC and reviewed by the EC. The EC requested that Takeda update the protocol. The EC letter stated, “Among the 16 subjects, 15 subjects in the open-label trial were known to have increased ALT and AST levels on Day 11 and the exposure was increased correspondingly in case of moderate hepatic impairment, indicating that repeated-dose drug administration had a certain impact on hepatic function, conversely, hepatic function also affected the in vivo behavior of drug. Therefore, it is unreasonable to collect samples for calculating terminal elimination constant (λz) and terminal half-life ($T_{1/2}$) only after single-dose administration; sample collection should also be carried out after multiple-dose administration.”

Takeda agrees to add PK sample collection at 36, 48, and 72 hours after the Day 10 dose to address this EC comment.

Pages 12 and 24, Study Summary: Study Design and Section 6.1

Existing Text

The pre-dosing study period will consist of a Screening Period (Study Days -28 to -2) and Check-in (Study Day -1). On Day 1, a single dose of TAK-491 or placebo will be administered followed by a pharmacokinetic sampling period through 72 hours postdose (Days 1-4). On Days 4 through 10, subjects will be on a daily dosing regimen, followed by a 24-hour pharmacokinetic assessment period prior to Study Exit (Day 11). The total confinement period for a subject who completes the study will be 12 days. All subjects will return to the site for follow-up serum chemistry tests on Day 14. A Follow-up telephone call will be made by the site at 14 (± 2) days following the last dose of study medication (Day 24 [± 2 days]) to inquire for any ongoing adverse events or serious adverse events (SAEs), new adverse events or SAEs, and concomitant medications taken since the final dose of study medication or Early Termination Visit.

A schematic of the study design is included as [Figure 6.a](#). A schedule of assessments is listed in [Appendix A](#).

Figure 6.a Schematic of Study Design

Screening	Check-in	Dosing and PK	72-hr PK	Dosing (a)	Dosing and AM Trough Level (b)	Dosing and 24-hr PK	Study Exit	F/U Visit (c)	F/U Call
Days -28 to -2	Day -1	Day 1	Days 2-4	Day 4	Days 5-9	Day 10	Day 11	Day 14	Day 24 (± 2)

PK=pharmacokinetics.

(a) Dosing will occur after the collection of the 72-hr pharmacokinetic sample.

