6.0 DETERMINATION OF SAMPLE SIZE

Total sample size of 64 subjects will be enrolled in this study. Sixteen subjects, 8 per regimen (TAK-491 40 mg and 80 mg), will be randomized to the open-label part of the study. Forty-eight subjects, 16 per regimen (TAK-491 40 mg, 80 mg and placebo), will be randomized to the double-blind part of the study. The sample size is considered sufficient for evaluation of safety, tolerability and PK of each part of the study, and was not based on statistical analysis power considerations.

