7.0 METHODS OF ANALYSIS AND PRESENTATION

7.1 General Principles

7.1.1 Summary Statistics and Precision

All tabulations of analysis results will include summaries by following regimens: TAK-491 40 mg (open-label), TAK-491 80 mg (open-label), TAK-491 40 mg (double-blind), TAK-491 80 mg (double-blind) and placebo (double-blind).

No formal statistical test will be performed in this study. Summaries will be based on descriptive analysis.

Means and medians will be presented to 1 more decimal place than the recorded data. The standard deviations (SDs) will be presented to 2 more decimal places than the recorded data. Exceptions may be made for derived data in the database where decimal precision is beyond necessary.

Where appropriate, variables will be summarized descriptively by study visit. For the categorical variables, the count and proportions of each possible value will be tabulated by regimen.

Percentages will be reported to 1 decimal place. For continuous variables, the number of subjects with non-missing values, mean, median, SD, minimum, and maximum values will be tabulated.

The data summaries will be accompanied by individual subjects data listings sorted by study part, regimen, and subject number. All data available from raw data will be listed. The actual day relative to the start of study drug will be determined and included in the listing.

Derived analysis datasets will be produced from raw data. This allows for convenient review of the data as well as any necessary supplemental analyses. All data from the raw data will be included in the derived datasets. Derived dataset specifications will be developed to include the names and definitions of derived variables in the derived SAS datasets. All analyses and data listings will be performed using the derived datasets.

Screen failure subjects will be grouped and listed.

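### The double-blind part was added to settle whether the ALT/AST rises are drug-related, but the SAP plans no dose-ordered ALT/AST estimate with a confidence interval and no display of ALT/AST against exposure

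*SAP*

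**What the plan says.** Protocol 6.2 explains the switch to a blinded, placebo-controlled design. Fifteen of the 16 open-label subjects had higher ALT and/or AST on Day 11 than on Day -1, and 7 of them were above the ULN. Diet and inactivity are offered as possible causes, but "a potential drug-related phenomenon has to be definitively ruled out". The ethics committee letter in protocol Appendix F adds that "repeated-dose drug administration had a certain impact on hepatic function, conversely, hepatic function also affected the in vivo behavior of drug".

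SAP 6.0 sets the numbers: "Forty-eight subjects, 16 per regimen (TAK-491 40 mg, 80 mg and placebo), will be randomized to the double-blind part of the study" and "Sixteen subjects, 8 per regimen (TAK-491 40 mg and 80 mg), will be randomized to the open-label part of the study". The sample size "was not based on statistical analysis power considerations".

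For laboratory data, SAP 7.11.2 lists summaries by part and regimen: "Baseline, postdose, and, change from baseline to postdose values for quantitative measurements", categorical urine results, markedly abnormal values and shifts against the normal range. SAP 7.11.5 adds a listing of liver-test data. For PK, SAP 7.9.2 says "Plasma and urine PK parameters of TAK-536 will be summarized by regimen using descriptive statistics", each part separately. SAP 7.9.3 (pharmacodynamics) and 7.10 (other outcomes) are marked not applicable. The general rule in SAP 7.1.1 is: "No formal statistical test will be performed in this study. Summaries will be based on descriptive analysis".

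**The concern.** The double-blind part has a specific question to answer: are the ALT/AST rises due to the drug or to confinement? Its planned liver output is a set of separate arm summaries. A reader of the study report would have to take differences between arms by eye, with no statement of how large a drug effect the data leave open. Ruling an effect out depends on that upper bound, and means with SDs do not state it.

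The trial also holds paired data that no output brings together. Each active subject has a 0-24 h profile from the Day 10 dose (SAP Table 7.a), which gives AUC24, and chemistry on Day 11 (protocol 9.3.8). Placebo subjects can be placed at zero exposure, with four assayed check samples each (protocol 9.1.12.1). At stake is whether the trial reports an interpretable answer to the question that prompted its redesign, or leaves that answer to analyses chosen after unblinding.

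**Working it through.** The documents give no effect size, SD, alpha or power for this question, so there is no planned figure to reproduce. The allocation adds up: 8×2 + 16×3 = 64.

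**1. What each planned output could show**

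| Output | What it gives | What it lacks for this question |
|---|---|---|
| Change from baseline (SAP 7.11.2) | A mean and SD per regimen | Difference, CI, baseline adjustment |
| Markedly abnormal values (SAP Appendix A) | Counts of ALT or AST >3×ULN | No open-label subject exceeded this on Day 11, so the Day 11 count would have been 0 of 16 |
| Shift table (SAP 7.11.2) | Moves across the ULN | 15 − 7 = 8 of the subjects with a rise were not above the ULN and would show no shift to high |
| PK parameters (SAP 7.9.2) | Exposure per regimen | Any laboratory variable |
| Listings (SAP 7.9.2, 7.11.2, 7.11.5) | Individual values | Any joint display |

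The pooled TAK-491 column is specified for adverse events (SAP 7.11.1), not for laboratory data.

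**2. Precision of the randomised estimates in the double-blind part**

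Let σ be the residual SD of log(Day 11/baseline), which the documents do not give. Normal quantiles are used, with no credit for baseline adjustment.

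- Pooled active minus placebo: SE = σ√(1/32 + 1/16) = 0.306σ. The 95% half-width is 1.96 × 0.306 = 0.60σ. Detectable at 80% power, two-sided 5%: 0.86σ.
- Each dose minus placebo: SE = σ√(2/16) = 0.354σ. Half-width 0.69σ; detectable 0.99σ.
- Trend scored 0, 1, 2: sum of squares 16 × (1 + 0 + 1) = 32, SE = σ/√32 = 0.177σ. Half-width 0.35σ per 40 mg.

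**3. Would a slope on individual AUC24 do better?**

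Assume mean exposure 1 at 40 mg and 2 at 80 mg (protocol 4.3 reports dose proportionality) and between-subject CV c, which is not in the documents. If the effect is linear in exposure, information in units of b²/σ² is:

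- Pooled contrast: 1.5²/(1/32 + 1/16) = 24.0.
- Dose trend: 32. Ratio 32/24 = 1.33.
- Exposure slope with placebo at 0: 32 + 80c². At c = 0.35 this is 32 + 9.8 = 41.8, ratio 1.74.
- Exposure slope in the 32 active subjects only: 32(0.25 + 2.5c²). This reaches 24 only when c² = 0.20, a CV of about 45%.

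That ranking depends on linearity. If the effect is the same size δ at both doses, the fitted trend is δ/2. Its information is 32 × δ²/4 = 8δ², against δ²/0.09375 = 10.7δ² for the pooled contrast, a ratio of 0.75.

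Simulated power (16/16/16, residual SD 1, CV 35%, two-sided 5%):

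| Assumed truth | Pooled contrast | Dose trend | Exposure slope, placebo = 0 |
|---|---|---|---|
| Linear, 0.45 SD per mean 40 mg exposure | 0.55 | 0.69 | 0.79 |
| Equal at both doses, same mean active effect (1.5 × 0.45 = 0.675 SD) | 0.57 | 0.45 | 0.36 |
| Saturating, half-maximal at 0.3 of mean 40 mg exposure | 0.80 | 0.72 | 0.64 |

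The third row should be read across only; its higher pooled power reflects a larger assumed mean effect. Over CV 20-50%, the exposure slope ranges over 0.74-0.86 in the linear case and 0.42-0.32 in the equal-effect case.

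**4. Can the slope mislead?**

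Exposure within a dose is not randomised. Protocol 4.3 reports 28% and 64% higher exposure in mild and moderate hepatic impairment, so liver function may drive exposure. With no drug effect and an assumed within-dose correlation of 0.3-0.5 between exposure and ALT change, the slope is significant in 11-23% of simulated trials at CV 35%. The randomised comparisons stay near 5%.

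A flat slope is also weak reassurance. In the equal-effect case it misses a real effect in 1 − 0.36 = 64% of trials. Among the 32 double-blind active subjects, a correlation below tanh(2.80/√29) = 0.48 is not detectable at 80% power.

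**The case against.** The strongest reply is that the SAP is descriptive by design and the sample size was not powered. Exposure-response is neither an objective nor an endpoint, and the protocol's chosen tool for causality is randomised placebo control. The by-regimen tables already put placebo, 40 mg and 80 mg side by side, so the dose order is visible. Individual PK and laboratory values are listed, and SAP 7.9.2 allows further PK analyses. Protocol 11.0 provides for unblinded aggregate liver review supported by an independent statistician.

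Much of this stands. There is no contradiction between the documents, and a reader who infers that the data go unused, or that arm means discard the dose order, goes too far. A reader might also infer that exposure is the most sensitive evidence on causality, or that a flat exposure slope would be stronger evidence of no effect than similar arm means. The documents give no dose-response shape, effect size or exposure CV to support either reading, and the working shows that both fail if the effect is flat or saturating. Nor did the ethics committee ask for an ALT-exposure analysis; it asked for sampling after multiple doses to obtain the terminal rate constant and half-life.

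The reply does not remove the gap. An estimate with a confidence interval is not a formal test and fits a descriptive plan. The optional clause for extra PK analyses names no liver variable and leaves the choice open until after unblinding. The protocol 11.0 review guards safety between cohorts; it is not a specified analysis for the report.

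**Conclusion.** The point holds in a limited form. For the question that the double-blind part was added to answer, the SAP plans no active-minus-placebo difference or dose trend in ALT/AST with a confidence interval, and no display of ALT/AST against exposure. The scheduled data support both.

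The main loss is the randomised estimate. It would carry a half-width of about 0.60 SD pooled, 0.69 SD per dose and 0.35 SD per 40 mg for the trend, so even when reported it would exclude only fairly large effects. That is a reason to state the interval. The exposure display is a useful secondary addition, not better evidence.

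The half-widths depend only on the arm sizes, full Day 11 data and a common SD. The power figures rest on assumed effect sizes, shapes and exposure CV. This is a worthwhile omission to repair, not an error in the plan.

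**What to change.** Add to SAP 7.11.2, for the double-blind part:

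- Model log(Day 11/baseline) for ALT and for AST, with log baseline as covariate, by randomised dose (0/40/80 mg). Report active minus placebo for each dose and pooled, and the dose trend, all with 95% CIs and back-transformed to ratios.
- Add one exploratory scatter plot of the log ratio against individual Day 10 AUC24, with placebo at 0 and open-label subjects as a separate stratum. Read it after the randomised estimates, and treat any slope as descriptive. Define its population explicitly, because placebo subjects with no measurable TAK-536 fall outside the Pharmacokinetic Set.
- State the limits. The slope gains power only if the effect is roughly linear in exposure, and loses to the pooled contrast if the effect is flat or saturating. Exposure within a dose is not randomised and may be altered by liver function. A flat slope does not by itself exclude a drug effect.

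Make the change before unblinding, in line with protocol 13.1; otherwise label the analysis post hoc. The cost is a short SAP paragraph, one model run for two enzymes and one figure, with no new data. The downside is a little more analysis work and an exploratory plot open to reverse causation.
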